5.3. Data Quality Assurance

Missing data fields will be queried upon initial entry into the web-based data collection tool. In addition to instant queries, periodic data quality reports will be sent to each site via the web-based data collection tool to permit entry of missing or incomplete data fields. Sites may also be asked to respond to data clarification requests. In the event that missing data are not reclaimed on query, each variable will be evaluated separately before each analysis. This evaluation is necessary to explore the reason for the missing data and to check for other known variables in the dataset that may predict why the data are missing.

6. Ethical Considerations and Trial Oversight

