9 GENERAL METHODOLOGY

Descriptive statistics will be grouped into three categories: Tele-rehab PT, Traditional PT, and Overall. Continuous variables will be summarized by the number of observations and the mean, standard deviation, median, minimum, and maximum values. For categorical data, the counts, denominators and percent per category will be presented within non-missing observations. Subjects with a missing value for a variable will not be included in the calculation for that variable. All continuous data will be summarized with one more significant digit than in the dataset. Percentages will be rounded to one digit to the right of the decimal. Subjects with missing categorical data will not be included in calculations of percentages for that variable unless otherwise specified. No imputation will be made for missing values. Both the frequency and the associated denominator will be shown to facilitate review of missing categorical data. Categorical responses of "Unknown" will be set to missing.

It is anticipated that both the 6- and 12-week follow-up calls will not occur exactly at 6 and 12 weeks post-op, respectively, for every patient. However, the DCRI Call Center is instructed to contact subjects as close as possible to the appropriate time since postoperative discharge date. Data needed for the primary endpoint will be prioritized if patients agree to spend only a limited time on the follow-up call.

All statistical tests will be one-sided (non-inferiority) or two-sided (superiority) with a significance level of 0.05, unless otherwise documented. Tests for differences between treatment groups for endpoints that are not protocol-specified may be performed. Unless otherwise stated, continuous variables will be compared between groups with two-sample student t-test or with Wilcoxon's rank-sum test depending on normality assumptions.

When it is necessary to detect differences between groups, unless it is stated otherwise, categorical values will be compared using the chi-square test or Fisher's exact test. The chi-square test will be used when all cells in the table of the categorical comparison have an expected value of 5 or above. Otherwise, a Fisher's exact test will be performed.

All tables will be presented with summary statistics overall and by treatment group unless otherwise specified.

All analyses will be completed using SAS version 9.4 or higher.

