9.4 Accounting for Missing Data

Missing data will not be imputed. We will analyze only available information.

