9.11.1 Effectiveness hypothesis (Non-Inferiority Test)

The tele-rehab intervention will be non-inferior to traditional PT at 6 weeks (differences between groups <5% for clinical and patient-reported outcomes) and 12 weeks (difference <5% patient-reported outcomes). The secondary objectives are to compare tele-rehab-supported PT and traditional PT on patient-centered outcomes as follows:

- 6 Weeks:
 - KOOS: Total score based on a normalized scale of 0-100 (worst to best). The minimal perceptible clinical improvement difference (MCID) for non-inferiority that we will use is 10 points.
 - ROM: This is reported to reflect both extension (lower) and flexion (upper) range of motion. An MCID is not available and based on recent literature we will use 6.3 degrees for extension and 9.6 degrees for flexion.
 - Gait Speed (m/sec): MCID is 0.1 m/s
- 12 Weeks:
 - KOOS: The minimal perceptible clinical improvement difference (MCID) for non-inferiority will be 10 points.

Analyses for each endpoint will be similar to those considered in Section 9.10 for the primary cost endpoint, except the tests will be one-sided for non-inferiority. A one-sided 95% confidence interval for the mean difference between intervention groups will be completed using parametric methods if possible; otherwise, the median difference will be utilized.

Non-inferiority will be determined if the upper bound of the difference indicative of treatment benefit in the control group is less than the MCID for each endpoint. No adjustment for multiple comparisons is necessary since all tests must be significant to determine non-inferiority (intersection-union multiple testing rule) for effectiveness.

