9.12 Other Exploratory Analyses

The final objectives (exploratory analyses) are to determine if superiority between PT methods exist for the endpoints primarily tested for non-inferiority, determine whether individual patient characteristics are associated with differential improvement from 6 to 12 weeks assessed by patient-reported outcomes, and to determine the cost for the VERA system such that the cost between the control group and intervention groups is cost-neutral, assuming that the intervention group is determined to cost less. The secondary endpoints that will be considered are detailed in Sections 7.2-7.4.

An appropriate regression model may be considered for the primary cost endpoint to adjust for baseline variables found to be imbalanced or to assess the influence of site on treatment effects. This will be done by adding a fixed-effect main site effect and interaction term between randomization strata (site) and treatment in a generalized linear model. Assuming the average cost for the intervention group is lower than the control group, we will also determine the cost for the VERA system such that the cost difference between the control group and the intervention group is cost-neutral.

If the endpoints tested for non-inferiority between PT methods are found to be non-inferior, then additional analyses to control for baseline covariates or site effects may be done using methods previously described to determine if the PT group is superior to the control group after adjustment.

To determine whether individual patient characteristics are associated with differential improvement, we will evaluate the change over time (0-6, 0-12 and/or 6-12 weeks) for endpoints measured at multiple time points using parametric or non-parametric methods previously discussed. When both 6 and 12-week assessment are made, the Sidak alpha-correction method will be used to correct for multiple comparisons. The correction method is given by $1-(1-\alpha)^{1/k}$, where k is the number of comparisons considered. If adjustments for baseline covariates are necessary, generalized repeated measures models will be used to assess main effects of intervention group and time, as well as the interaction between time and intervention groups.

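### The 12-week KOOS and pain non-inferiority tests use available cases only and ignore the 6-week score, so they would lean toward non-inferiority if poor recoverers are lost more often on tele-rehab; the SAP also omits the Protocol 5.3 missingness check.

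*Protocol*

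**What the plan says.** Protocol 5.3 (Data Quality Assurance) says that where queries do not recover missing data, "each variable will be evaluated separately before each analysis". It gives the purpose: "This evaluation is necessary to explore the reason for the missing data and to check for other known variables in the dataset" that might explain the missingness.

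SAP 9.4 is the whole missing-data plan: "Missing data will not be imputed. We will analyze only available information". SAP 9 agrees: "No imputation will be made for missing values", and "Subjects with a missing value for a variable will not be included in the calculation for that variable".

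For the effectiveness non-inferiority tests, SAP 9.11.1 says "Analyses for each endpoint will be similar to those considered in Section 9.10 for the primary cost endpoint", made one-sided. SAP 9.11.2 handles pain with a one-sided 95% confidence interval for the group difference. The 12-week margins are 10 points for KOOS and 1.7 for pain. The level comes from SAP 9: "All statistical tests will be one-sided (non-inferiority) or two-sided (superiority) with a significance level of 0.05, unless otherwise documented".

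Both outcomes are also collected at 6 weeks (SAP 9.8.2). A longitudinal model appears only among the exploratory analyses of SAP 9.12, and only if baseline adjustment is needed: "generalized repeated measures models will be used to assess main effects of intervention group and time". SAP 10, which lists departures from the protocol, declares only the change of margins.

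**The concern.** A patient who gives KOOS and pain at 6 weeks but not at 12 contributes nothing to the 12-week tests, although the 6-week score is likely to be a strong predictor of the missing one. Leaving it out is harmless if loss at 12 weeks is unrelated to recovery, or related to it in the same way in both arms. If poor recoverers are lost more often on tele-rehab, the observed tele-rehab mean is too favourable, the deficit is understated, and the confidence bound falls inside the margin too often. In a non-inferiority comparison this error favours the new treatment.

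Missing 12-week scores are plausible on the plan's own terms. SAP 9 puts the cost data first when a patient allows only a short call, and SAP 9.8.3 bars KOOS junior from the 12-week efficacy analysis. The trial is open-label and the arms differ in how therapists see patients, so equal loss cannot be taken for granted. The Protocol 5.3 check would show whether loss is in fact unequal, and the SAP does not schedule it.

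**Working it through.** **The plan's own figures.** The documents give no SD, visit correlation, dropout rate or power for KOOS or pain. The only power figures are for cost. Protocol 5.1 states 0.8023 for effect size 0.3255 with 150 per arm, and the noncentral t with 298 df reproduces 0.8023. That figure has no bearing on this point.

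**Inputs from the documents.** 150 per arm (Protocol 3.4); margins 10 and 1.7, and one-sided 95% bounds (SAP 9.11).

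**Assumed inputs.** KOOS SD 15-20, pain SD 2-2.5, 6-to-12-week correlation ρ 0.5-0.7, dropout 0-20% per arm.

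**Formulas.** Suppose dropout depends on the 6-week score. Let δ be how far the completers' 6-week mean lies on the better side of their whole arm's 6-week mean, in SD units. Then:

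- bias toward non-inferiority = ρ × SD × (δ_tele − δ_control)
- SE = SD × √(1/n_tele + 1/n_control), counting completers
- false-claim rate with the true deficit at the margin ≈ Φ(−1.645 + bias/SE)

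**Simulation.** 3,000 trials per setting, with the true deficit set at the margin, so the correct rate is 5%. The log-odds of dropout rise by 1.5 per SD of worse 6-week score, which is steep (odds ratio e^1.5 ≈ 4.5). The last column is a likelihood estimate that uses the 6-week value.

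| Endpoint | Missing, tele-rehab / control | Bias toward non-inferiority | False claims, available cases | False claims, using 6-week value |
|---|---|---|---|---|
| KOOS | 10% / 0% | 0.95-1.73 | 13-18% | 5.1-6.3% |
| KOOS | 20% / 0% | 1.64-3.15 | 22-38% | 5.0-5.9% |
| KOOS | 20% / 10% | 0.81-1.42 | 12-15% | 4.4-6.1% |
| KOOS | equal, 10% or 20% | within ±0.07 | 4.5-5.4% | 4.5-5.4% |
| Pain | 10% / 0% | 0.13-0.21 | 13-19% | 4.8-5.6% |
| Pain | 20% / 10% | 0.10-0.18 | 11-16% | 4.8-5.2% |
| Pain | 20% / 20% | about 0 | 4.8-5.2% | 4.3-5.0% |

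**Hand check, KOOS.** SD 15, ρ 0.5, 10% / 0%. A bias of 0.95 implies δ = 0.95/(0.5 × 15) = 0.127. SE = 15 × √(1/135 + 1/150) = 1.78. Φ(−1.645 + 0.95/1.78) = Φ(−1.11) = 0.13, against 13.2% simulated.

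**Hand check, pain.** SD 2.5, ρ 0.7, 10% / 0%. SE = 2.5 × √(1/135 + 1/150) = 0.297. Φ(−1.645 + 0.21/0.297) = Φ(−0.94) = 0.17, against 18% simulated.

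**Milder selection.** With KOOS SD 18, pain SD 2.3, about 20% missing and score-dependent dropout on tele-rehab only, the available-case rate is 12-29% for KOOS and 13-29% for pain. The two-visit likelihood estimate gives about 4-6%.

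**Selection in both arms.** KOOS SD 18, log-odds slope 1.0 per SD on tele-rehab and 0.5 on control: 11%. Equal slopes: 4.3-5.2%.

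**Joint requirement for KOOS.** With a 10-point deficit at both visits, 12-week KOOS alone passed in 8.5% of trials (slope 0.5, ρ 0.6) and 33% (slope 1.0, ρ 0.7). Both KOOS visits passed in 2.1% and 4.2%. With no deficit at 6 weeks and the full 10 points at 12, the joint rate was 34%.

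**Limits.** With no true difference (KOOS SD 20, 10% missing in each arm), non-inferiority is declared in over 99% of trials by either method. If dropout follows the unseen 12-week value (KOOS SD 15, ρ 0.6, 20% / 10%), using the 6-week value lowers the false-claim rate only from 24% to 16%.

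**The case against.** **No contradiction between the documents.** Protocol 5.3 is a data-quality section that deals largely with the web data tool, whereas 12-week KOOS and pain come from the call center. It asks for an evaluation and prescribes no model or imputation. A reader might infer that the SAP contradicts the protocol, or that the protocol demands a longitudinal model. Neither is supported: the SAP omits the evaluation without forbidding it. What remains is that the protocol's wording covers every variable and every analysis, and the SAP gives the step no place.

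**Differential dropout is assumed.** A reader might infer from the open-label design that tele-rehab will lose its poor recoverers. The documents do not show this. One call center follows both arms, days, nights and weekends, with alternate contacts on file and reimbursement tied to study benchmarks. Tele-rehab patients are monitored remotely and can be sent for in-person visits, while some controls may have only printed instructions. This stands, so every inflated rate above is conditional.

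**The intersection-union rule protects KOOS.** A reader might carry the 12-week rate over to the whole effectiveness claim. That fails when the deficit is already present at 6 weeks, because 6-week KOOS must also pass, as must range of motion and gait speed. It does not cover a deficit that emerges after 6 weeks. Pain has no 6-week non-inferiority test; falls and re-hospitalizations must also pass, but they measure other things.

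**A mixed model is not a full cure.** This is correct. It relies on missingness being explained by observed data, and KOOS junior is allowed at 6 weeks, so a common KOOS score may not exist for every patient. The fix has to deal with both.

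**Conclusion.** The point holds in conditional form. The 12-week KOOS and pain tests discard collected 6-week information, and the SAP does not carry forward the protocol's check on predictors of missingness. If selective loss is greater on tele-rehab, the false-claim rate for the single endpoint rises from 5% to roughly 12-30% (KOOS SD 18, pain SD 2.3, about 20% missing, all assumed). It is lower where control loss is also selective. With equal selective loss, or a true difference near zero, there is little or no effect. The exposure is greatest for 12-week pain and for a KOOS deficit that appears after 6 weeks. The documents do not show that dropout will differ between arms, nor that a non-inferiority conclusion from this trial would be wrong. The change is worth making because it uses data already collected.

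**What to change.** 1. In SAP 9.11.1 and 9.11.2, estimate the KOOS and pain contrasts from a repeated-measures likelihood model. Outcomes are the 6- and 12-week values; terms are arm, visit, arm-by-visit, site, and baseline score where collected, with unstructured covariance. Compare the one-sided 95% bounds with the existing margins. Nothing is imputed, so the rule in SAP 9.4 can stand for the main analysis.
2. For KOOS, use one score that can be computed at both visits. Where only KOOS junior was taken at 6 weeks, use it as a covariate for the full 12-week KOOS instead.
3. Add the Protocol 5.3 check to SAP 9.4 as a table of missing 12-week values by arm and 6-week score.
4. Add a tipping-point sensitivity analysis for 12-week KOOS and pain, because the model does not remove bias from dropout driven by the unseen 12-week value.

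Cost: SAP wording, a standard SAS mixed model, one table and one sensitivity analysis, with no new data or patients. The downside is slightly more modelling than a t-test and reliance on missing-at-random in the main analysis. Power at no true difference was 99.7% for either method in simulation (KOOS SD 18).

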6.1. Ethical Considerations

This trial will be submitted to an IEC or IRB (local or central) for approval. Minimum supporting documentation includes the final protocol, informed consent form, data collection forms, surveys and interview scripts, and applicable patient recruitment materials. Progress reports will be submitted to IRBs and regulatory authorities as required by local laws and regulations. This trial will be conducted in accordance with the ethical principles that have their origin in the Declaration of Helsinki and are consistent with good clinical practices and applicable laws and regulations of the institution where the trial is being conducted, as appropriate.

As part of local IRB submission for the study, sites will be expected to outline their proposed methods and timeline for completing procedures to assess patient interest and pre-screen for eligibility. Sites also will be expected to obtain IRB approval for verbally consenting the patient before completing the RAPT score assessment in order to determine eligibility.

The patient will provide authorization for the uses and disclosure of their personal health information as described in the informed consent form. The confidential nature of the patient information will be maintained.

6.2. Trial Oversight

Trial operation management and scientific oversight for VERITAS will be performed by Duke Clinical Research Institute (DCRI). Sites will be provided with both telephone numbers and email addresses, as appropriate, to contact the DCRI study team for assistance, which generally will be available from 8 am – 5 pm Eastern Time Monday through Friday, excluding holidays.

Throughout the study, DCRI will maintain records of all issues and resolutions when a site is assisted.

6.3. Trial Leadership

Duke University and Duke Clinical Research Institute (DCRI), along with the sponsor, Reflexion Inc., will be responsible for VERITAS design, implementation, and leadership. Data analysis and publications will be managed according to a written plan designed to maintain appropriate scientific oversight and rigor.

7. Administrative Requirements

7.1. Study Completion

Study enrollment will continue until 300 patients have been enrolled. Enrollment is anticipated to last approximately 10 months. The study will be considered complete upon completion of all study-related procedures (data collection) for the last patient enrolled.

7.2 Adverse Experience Reporting

Reporting of any adverse experiences discovered during the course of the study will be the responsibility of care providers at the site, and should be made using the appropriate mechanism (e.g., FDA Medwatch).

7.3. Source Documentation

At a minimum, source documentation must be available to substantiate patient identification, eligibility, participation, and proper informed consent procedures. Specific items required as source documents will be reviewed with the investigator before the study.

7.4 Patient Reimbursement

Patients will be reimbursed for their time in participating in this study, based on completion of study benchmarks. Funds for patient reimbursement will be provided to participating sites, who in turn will issue reimbursement directly to their enrolled patients, as appropriate. Details of the reimbursement schedule and requirements will be detailed in the site-specific informed consent document.

1 MODIFICATIONS TO ORIGINAL SAP

- Section 9.10 (page 23): Corrected costs assigned to PT visits in Control group cost formula from \$210 to \$133, to match costs listed in table above

2 LIST OF ABBREVIATIONS

Abbreviation	Description
6MWT	Six minute walk test (i.e., distance walked in 6 minutes)
AE	Adverse Event
ANOVA	Analysis of Variance
BMI	Body Mass Index
CRF	Case Report Form
D/C	Discharge
DCRI	Duke Clinical Research Institute
DMC	Data Monitoring Committee
DUMC	Duke University Medical Center
ER	Emergency Room
GCP	Good Clinical Practice
IC	Informed Consent
IRB	Internal Review Board
ITT	Intent-to-Treat
KG	Kilogram
KOOS	Knee Injury and Osteoarthritis Outcome Score
M	Meter
MCID	Minimal Clinical Improvement Difference
MITT	Modified Intent-to-Treat
PI	Principal Investigator
POST-OP	Postoperative
PT	Physical Therapy / Physical Therapist
PROMIS	Patient-Reported Outcomes Measurement Information System
QC	Quality Control
QOL	Quality of Life
ROM	Range of Motion
SAE	Serious Adverse Event
SAP	Statistical Analysis Plan
SC	Steering Committee
SAP	Statistical Analysis Plan
SOC	Standard of Care
SOP	Statistical Operating Procedure
TKR	Total Knee Replacement
US	United States
Vera™	Virtual Physical Therapy Delivery System

3 **QUALITY CONTROL**

All tables, listings, and graphs will be reviewed by the lead and faculty statisticians before considered final. The quality control process will ensure that the numbers are produced by a statistically valid method and that the execution of the computations is correct. While independent programming (second verification) will not be done, tables will be reviewed for accuracy, consistency with this analysis plan, consistency within tables, and consistency with corresponding output.

4 PURPOSE AND SCOPE OF STATISTICAL ANALYSIS PLAN

The purpose of this analysis plan is to provide a framework in which answers to the protocol objectives may be achieved in a statistically rigorous manner. Specifically, this plan will:

- Give a brief overview of the protocol, study design and study objectives
- Outline the types of analyses and presentations of data that are relevant to the primary and secondary study objectives (efficacy and safety)
- Explain how the data are analyzed, adhering to commonly accepted standards and practices of statistical analysis

The scope of this plan applies to the analyses as presented in the clinical protocol only and does not include any analyses for exploratory purposes. Documents used in the preparation of this statistical analysis plan include the study protocol (Final Protocol dated March 2, 2017) and Case Report Forms (CRF) including Randomization (dated August 17, 2016), Baseline Data (October 17, 2016), Baseline Survey (dated August 17, 2016), Discharge (dated August 17, 2016), 6-week Data (dated August 17, 2106), 6-week Survey (dated February 5, 2017), 3-month Survey (dated February 5, 2017), and Patient Diary (dated August 17, 2016). The statistical plan described is an *a priori* plan and no analyses or data review by randomized treatment group prior to the preparation of this plan have been conducted. The Duke Clinical Research Institute (DCRI) will oversee all statistical analyses detailed in this analysis plan. This document defines the populations to be analyzed and provides full details of the statistical analyses, data displays, and algorithms to be used for data derivations to aid in the production of the statistical output.

5 OVERVIEW

As background for the statistical methods presented below, this section provides an overview of the study objectives and design. It must be understood that this overview is a summary only, and that the protocol is the definitive reference for all matters discussed in what follows.

